- Presence of one or more of the following physiological states: systolic BP <90 mmHg, or MAP <65 mmHg, or increasing need for vasopressor drug infusion or pulse pressure variation >12 % or stroke volume variation >12%, or Cardiac index <2.2 L/min/m² or heart rate >100 or urinary output <20 ml/hr or either rising lactate levels or lactate levels >2 mmol/L or capillary refill time >3 seconds or central venous pressure <8 mmHg.

Exclusion criteria

- Confirmed or suspected pregnancy
- Patients with traumatic brain injury
- Active bleeding
- Haemoglobin level <70 g/L

• People who refuse blood products SWIPE Protocol UK V2.2, dated 18th May 2016 EudraCT No: 2016-001940, UK Protocol ID: R04336 • Patients in whom death is considered imminent (within 24 hours)

Sample size estimate

Given that in the first 48 hours the 5% albumin administered in the SAFE study [14] was a total of 1785ml (SD of 1865), we will aim to detect a decrease in fluid given to 1300ml (SD of 1368: proportionately the same as that seen in SAFE for a mean inout of 1785ml). This decrease of around 500ml in fluid input is considered of potential clinical value. To have a 90% power of detecting such a difference at an alpha level of 0.05, 195 patients will need to be randomised to each group. We have rounded this number up to 200 in each group to account for possible data loss.

Randomisation procedure

- Computer generated sets of random allocations will be produced by the Research Co-ordinator in advance of the study.
- Randomization will be by means of sealed envelopes with permuted blocks of variable size.
- Each envelope will contain a study arm allocation as well as a copy of a simplified version of the study protocol.
- Every patient who participates in any study related procedure will be assigned a unique patient number.

Intervention description

Patients will be randomised one of two arms:

• The treatment arm will receive an intravenous infusion of 20% albumin (Alburex

20®, CSL Behring, Marburg, Germany) every time the treating clinician decides SWIPE Protocol UK V2.2, dated 18th May 2016 EudraCT No: 2016-001940, UK Protocol ID: R04336 that a fluid bolus needs to be given during the first 48 hours in ICU. The treating clinician determines the volume and infusion rate of each fluid bolus.

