- Reason for admission to intensive care (post-operative complication, sepsis, medical emergency, post-operative management, other) and urgency (planned, unplanned, emergency). If surgical, date and type of operation.
- Weight and height on admission, to be used for calculation of body surface area.

Clinical Data

- Haemodynamic data: HR, ABP, CVP will be measured hourly during the study period.
- Blood gas results: PaO₂, lactate concentration, pH/H+ concentration, bicarbonate concentration, sodium concentration, chloride concentration, creatinine concentration, haemoglobin concentration and base deficit/excess will be measured hourly during the study period.
- Fluid balance Resuscitation fluids. Each fluid bolus will be recorded (type of resuscitation fluid, volume, infusion speed).

• Fluid balance – for each day or part there of. SWIPE Protocol UK V2.2, dated 18th May 2016 EudraCT No: 2016-001940, UK Protocol ID: R04336

- Baseline serum creatinine and urea pre-admission to ICU if available. Defined as
 a serum creatinine and urea taken in the six months pre-admission to hospital for
 this ICU event.
- Serum creatinine on admission, as indicated above, and as indicated clinically.
- Serum albumin on admission and as indicated clinically.
- Doses of furosemide administered (or rate of furosemide infusion).
- Doses of vasopressors and inotropes administered (or infusion rates).
- All other biochemical and haematological indices recorded as clinically indicated during the patient admission.

Outcome Data

- Primary efficacy outcome
 - Amount of resuscitation fluid (mL) administered over the first 48 hours in ICU.
- Secondary efficacy outcomes
 - The cumulative fluid balance after 48 hours in ICU.
 - The amount of vasoactive medication given over the first 4 hours after a fluid bolus and over the first 48 hours in ICU.
 - The total amount of fluids given over the first 4 hours after a fluid bolus,
 daily and over the first 48 hours in ICU.
 - The relative change in haemodynamic variables and blood gas results over the first 4 hours after a fluid bolus.
 - The relative change between baseline and peak creatinine in the first 48

hours after randomization.

- Patient-centred efficacy outcomes
 - Need for RRT
 - Renal status at 90 days
 - Hours on mechanical ventilation
 - ICU discharge status (alive or dead)
 - ICU length of stay
 - Hospital discharge status (alive or dead)

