 - Hospital outcome (discharge destination home, another hospital, advanced care institution)
 - Hospital length of stay (date of discharge)
 - Mortality status at 90 days.
- Feasibility and safety outcomes:
 - Distribution of values for primary and secondary outcome
 - Randomized / Screened patients ratio
 - Data completion rate
 - Loss to follow-up rate
 - Recruitment rate and duration
 - Separation in amount of fluid given

Safety outcomes

- Development of side-effects
- Episodes of hypotension
- Development of kidney failure

o Adverse changes in any of the physiological efficacy measures

Data analysis

Outcomes will be compared after log transformation where appropriate. Comparisons will be made using t-test and ANOVA for repeated-measures or Wilcoxon rank-signed test and Kruskall-Wallis according to the underlying distribution for continuous data and Chi-square for categorical data. A Kaplan-Meier curve with log-rank test will be performed to further compare in-hospital mortality and rate of discharge home. Logistic regression analysis will also be performed to adjust for baseline imbalances. Analysis will be an on intention-to-treat basis.

Risks and Benefits

Albumin solutions have been used for resuscitation since the 1940s. An investigation of the safety of albumin solutions showed that between 1998 and 2000, approximately 10⁷ units of such albumin solutions were administered worldwide. Adverse effects that were directly associated with albumin were an extremely rare event during this observation period [15]. There are, however, more recent reports that the use of (20%) albumin is associated with increased mortality for patients with traumatic brain injury [6]. Accordingly, patients with traumatic brain injury will be excluded from the SWIPE study. Although albumin is prepared from pooled plasma, albumin preparations currently available are considered to be non-allergenic due to the manufacturing process.

Data handling, retention, storage and destruction

Data handling

The case report form (CRF) will be developed by the members of the investigator team as a paper CRF. All data will be collected by members of the investigator team as described in the CRFs from the source data. Information recorded in the CRF should accurately reflect the subject's medical/hospital notes and must be completed as soon as it is made available.

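### The discharge-destination outcome has no category for patients who die in hospital, so its chi-square comparison as defined holds hospital survivors only, at odds with intention to treat.

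*Protocol*

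**What the plan says.** Under Data collection, Outcome Data, the patient-centred efficacy outcomes include "Hospital outcome (discharge destination home, another hospital, advanced care institution". These are the only three values given. The opening of the Data collection section makes the items that follow the content of the case report form, so the list also describes the data field.

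Death is recorded as separate outcomes in the same list, among them "Hospital discharge status (alive or dead" and "Mortality status at 90 days". The list also contains "Renal status at 90 days", with no categories or definition.

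The Data analysis section gives the test, "Chi-square for categorical data", and the basis, "Analysis will be an on intention-to-treat basis". It adds a time-to-event analysis: "A Kaplan-Meier curve with log-rank test will be performed to further compare in-hospital mortality and rate of discharge home". It does not say how deaths enter the destination table or the discharge-home curve.

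**The concern.** Comparing destinations only among patients who leave hospital alive conditions on something that happens after randomisation. If treatment changes who survives, the two groups of survivors are no longer comparable. The protocol's introductory summary puts forward lower mortality as a possible consequence of giving less fluid, so the trial's own rationale allows for this.

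The distortion can run either way. If one arm keeps alive some very sick patients who would otherwise have died, those patients are less likely to go home, and the arm looks worse among survivors. If one arm has more deaths, its remaining survivors are a fitter group and it looks better. The item is labelled an efficacy outcome, so readers would take the comparison as evidence of benefit or harm.

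**Working it through.** **Step 1: the text.** The outcome has three values, all for live discharge. The test is chi-square on categories. The basis is intention to treat, meaning all randomised patients in their allocated arm. A patient who dies in hospital belongs to the analysis set but has no value on the outcome. The table as defined can therefore hold only hospital survivors. The separate alive-or-dead item supplies the missing information, but no sentence brings it into this table.

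**Step 2: inputs.** The protocol states no figure for this outcome to reproduce. The Sample size estimate gives 200 per arm. Mortality and discharge-home rates are not given, so every rate below is assumed. The direction of the mortality difference is also assumed and says nothing about either product. At 10% to 30% mortality, 400 × 0.10 = 40 to 400 × 0.30 = 120 patients would have no category.

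**Step 3: formula.** Let *h* be the share of all randomised patients discharged home alive and *m* the share who die in hospital. Among survivors the share going home is *h* / (1 − *m*). If *m* is equal in both arms, the direction is preserved and the difference is only scaled by 1 / (1 − *m*). If *m* differs, the direction can change.

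**Step 4: results, 200 per arm, 5% albumin versus 20% albumin.**

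| Deaths (assumed) | Home, all randomised | Home, survivors only | Survivors-only difference |
|---|---|---|---|
| 10% v 15% | 50% v 50% | 100/180 = 55.6% v 100/170 = 58.8% | +3.3 points |
| 15% v 20% | 50% v 50% | 100/170 = 58.8% v 100/160 = 62.5% | +3.7 |
| 20% v 25% | 50% v 50% | 100/160 = 62.5% v 100/150 = 66.7% | +4.2 |
| 25% v 30% | 50% v 50% | 100/150 = 66.7% v 100/140 = 71.4% | +4.8 |
| 20% v 25% | 50% v 48% | 100/160 = 62.5% v 96/150 = 64.0% | +1.5 (all randomised: −2.0) |
| 25% v 20% | 110/200 = 55.0% v 112/200 = 56.0% | 110/150 = 73.3% v 112/160 = 70.0% | −3.3 (all randomised: +1.0) |

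In the first four rows there is no difference in the share going home, yet the arm with more deaths appears better. In the last two rows the sign reverses, once in each direction.

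**Step 5: against sampling error.** In the third row the pooled share is 200/310 = 0.645, and the standard error of the difference is √(0.645 × 0.355 × (1/160 + 1/150)) = 0.054, or 5.4 points. The artefact of 4.2 points is 4.2/5.4 ≈ 0.8 standard errors.

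**Step 6: the time-to-event analysis.** This can start from all randomised patients, but a conventional Kaplan-Meier analysis would censor deaths at the time of death, treating those patients as if they could still go home. Take the third row in the limiting case where all deaths precede the first discharge home and patients discharged elsewhere stay in the risk set. The estimated probabilities of going home are then 1 − 60/160 = 62.5% and 1 − 50/150 = 66.7%, the survivors-only figures. Giving deaths a permanent never-discharged-home status restores 50% in each arm.

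**The case against.** **Nothing in the protocol announces a survivors-only comparison.** That is correct. It names no survivor subset, states no denominator and claims intention to treat. A reader might infer that the investigators have decided to analyse survivors; the documents do not support that. What stands is narrower: the closed list of categories yields that table if it is followed as written.

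**Handling of deaths in a non-primary outcome is commonly left to the SAP, which is not shown.** This would dispose of a complaint resting only on silence. Here the protocol itself gives a list of values that omits a possible result and pairs it with a stated test and basis.

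**Death is collected next to this item.** It is, and status followed by destination is an ordinary form layout. This makes the repair cheap, but it does not put deaths into the comparison.

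**Discharge home is also analysed by Kaplan-Meier and log-rank.** True, and that analysis need not exclude anyone. But it is an additional comparison, it has no rule for deaths, and it does not repair the chi-square table.

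**Early deaths are limited by eligibility.** Patients expected to die within 24 hours are excluded. Later hospital deaths remain possible in an ICU population.

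**The size is constructed, and the reversals are among null results.** Both points stand. In the last row of the table, an uncorrected chi-square gives p = 0.52 among survivors and p = 0.84 over all randomised patients. Mortality would also be reported, so a careful reader could see the problem.

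**Extending the point to 90-day renal status.** A reader might infer the same error there, since a dead patient has no kidney function to classify. The protocol gives that outcome no categories, so the text does not show that deaths are left out, and a SAP may define it. No error is shown.

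**Conclusion.** The point holds for discharge destination. The outcome as defined cannot classify in-hospital deaths, so its chi-square comparison is conditional on survival and conflicts with the stated intention-to-treat basis. The size is unknown from the documents. Under the assumed rates, a 5-point difference in mortality with equal shares going home gives a spurious 3.3 to 4.8 points in favour of the arm with more deaths. This depends on mortality differing between arms; with equal mortality the direction is not affected. The outcome is neither primary nor secondary, and the primary comparison of fluid volume is untouched. The correction is worth making, but the point does not threaten the trial's main conclusion.

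**What to change.** In Outcome Data, add *died in hospital* as a fourth category of hospital outcome, filled from the hospital discharge status already collected. In Data analysis, state that *discharged home alive* is compared with all randomised patients as the denominator, and show all four categories by arm. For the time-to-discharge-home analysis, state that deaths are not censored at the time of death but handled as a competing event, so that a patient who dies is counted as never discharged home.

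The cost is wording and one added category, taken through the protocol's own amendment route; no new data are needed. The small downside is that the measure then partly reflects mortality, which is why all four categories should be shown.

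For 90-day renal status, showing death by day 90 as its own state alongside renal status is a suggestion only. Replacing that outcome with a composite of death or renal replacement therapy is not required; it would change the question being asked.

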- We hypothesise that a lower volume of resuscitation fluid will be administered over the first 4 and 48 hours in ICU in patients receiving 20% albumin than in patients receiving 5% albumin.
- We hypothesise that the cumulative fluid balance over the first 48 hours in ICU will be significantly lower in patients receiving 20% albumin than in patients receiving 5% albumin.
- We hypothesise that the administration of 20% albumin will create a significantly greater increase in the hourly and mean arterial blood pressures over the study period compared to the 5% albumin.

- We hypothesise that the mean central venous pressure will be significantly lower in patients receiving 20% albumin than in those patients receiving 5% albumin.
- We hypothesise that patients receiving 20% albumin will require less vasoactive medications over the study period as compared to patients receiving 5% albumin.
- We hypothesise that the overall administration of chloride will be less in patients receiving 20% albumin than in patients receiving 5% albumin.
- We hypothesise that 20% albumin administration will significantly reduce peak serum creatinine in the first 48 hours following randomisation when compared to 5% albumin administration.
- Finally, we hypothesise that the administration of 20% albumin will significantly increase the PaO₂/FiO₂ ratio when compared to the administration of 5% albumin.

Relevance and Importance

- The association between fluid accumulation and poor patient outcomes has been established.
- Fluid resuscitation with 20% albumin may reduce the volume of fluid administration.
- A reduced volume of fluid administered during critical illness may achieve similar hemodynamic improvements without the need for additional volume administration

Methodology

Study design

The SWIPE study is an investigator-initiated, multi-centred, open label, randomisedcontrolled trial.

Participant recruitment and selection

All patients will be recruited if they meet the inclusion criteria and no exclusion criteria.

Inclusion criteria

- Admitted to the intensive care unit at participating sites for less than 24 hours.
- Age 18 years or greater
- Need for fluid bolus as determined by the treating clinician

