The control arm will receive an intravenous infusion of 5% albumin (Alburex 5[®], CSL Behring, Marburg, Germany) every time the treating clinician decides that a fluid bolus needs to be given during the first 48 hours in ICU. The treating clinician determines the volume and infusion rate of each fluid bolus.

Randomised participants in this study will receive and infusion of 20% albumin (treatment group) or 5% albumin (control group) each time the treating physician decides that a fluid bolus needs to be given during the first 48 hours of ICU. The treating clinician determines the volume and infusion rate of each bolus. Other fluids (nutrition, drug infusions, blood products) are given as per the discretion of the treating clinician.

Blinding

Blinding in this trial is not possible as Alburex $20^{\$}$ comes in 100 mL glass bottles whereas Alburex $5^{\$}$ comes in 500 mL bottles.

Monitoring

- Routine clinical monitoring shall continue after recruitment to the study.
- Routine monitoring of critically ill patients admitted to the ICU includes:
 - Heart rate (HR)
 - Arterial blood pressure (ABP)
 - Central venous pressure (CVP)

Oxygen saturation (SpO₂)
 SWIPE Protocol UK V2.2, dated 18th May 2016
 EudraCT No: 2016-001940, UK Protocol ID: R04336

- Urine output (UO)
- Respiratory rate (RR)
- Temperature
- o Fluid intake
- Fluid output
- Ventilator settings
- Blood gas results
- Serum creatinine
- Serum albumin

Patient Care

- Participation in the study shall not affect patient treatment in any other way.
- All additional therapies shall be administered at the discretion of the treating clinician.
- These therapies include:
 - Oxygen therapy
 - Antibiotics
 - Radiological investigations
 - Surgical interventions

There will be no attempt to control any other treatment. In particular there will be no attempt to control vasopressor therapy, oxygen therapy, antibiotics, blood, blood products and surgical intervention.

Data collection

The case report form will collect the information detailed below. The electronic medical records and previous volumes of notes will be accessed to collect baseline data where appropriate. Laboratory data will be accessed to acquire the items detailed below. We will perform a data review after the first 20 patients to ensure our data capture strategy is appropriate.

Data will be collected on the following variables:

Patient data

- Code for patient, gender and age. Date of admission to ICU and to hospital.

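### Repeated-measures ANOVA, the method named for serial readings, is poorly matched to the hypothesis of a greater rise in blood pressure; a baseline-adjusted contrast over a stated window would serve better

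*Protocol*

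**What the plan says.** The Hypotheses section expects 20% albumin to produce a "significantly greater increase in the hourly and mean arterial blood pressures over the study period". Under Data collection, Clinical Data, the protocol states: "Haemodynamic data: HR, ABP, CVP will be measured hourly during the study period". Blood gas variables follow the same hourly schedule.

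The Data analysis section covers all continuous outcomes in one sentence. The parametric part is "Comparisons will be made using t-test and ANOVA for repeated-measures". The alternative is "or Wilcoxon rank-signed test and Kruskall-Wallis according to the underlying distribution for continuous data". The only covariate adjustment named is logistic regression, which does not apply to a continuous pressure. The section closes with "Analysis will be an on intention-to-treat basis".

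The window differs between sections. Aims sets arterial and central venous pressure at the first 4 hours. The haemodynamic and blood gas outcome under Outcome Data is a relative change over the 4 hours after a bolus. The hypothesis runs over the study period, and treatment is given whenever the clinician decides "that a fluid bolus needs to be given during the first 48 hours in ICU".

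**The concern.** A two-arm repeated-measures ANOVA has two terms that compare the arms.

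- **Arm main effect.** It compares average level. If the pre-treatment reading is in the series, it dilutes the effect. If it is left out, the baseline information is not used.
- **Arm-by-time.** This is the term closest to a greater increase, but it is an omnibus test of profile shape, with 4 numerator degrees of freedom for readings at 0-4 h and 48 for 0-48 h. Its uncorrected F test also assumes sphericity (equal variance of the difference between any two hours), which serially correlated readings violate.

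Neither term is a directed, baseline-adjusted test of a sustained rise. The classical form also needs a complete series from each patient, which sits badly with intention-to-treat in an ICU population that dies, is discharged or misses readings. At stake is the physiological efficacy part of the trial: blood pressure, central venous pressure, heart rate and blood gases.

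**Working it through.** The protocol gives no error rate or power for these comparisons, so there is no stated figure to reproduce.

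**Inputs.** From the protocol: 200 per arm, hourly readings, windows of 0-4 h (5 readings) or 0-48 h (49 readings). Assumed, because the protocol gives no values: two-sided 5%; unit-variance readings with correlation s + (1-s)ρ^|j-k| between hours j and k; ρ = 0.5 to 0.9; s (share of variance constant within patient) = 0 or 0.3; a rise of 0.25 SD at every post-baseline hour.

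**Power formulas.** Let V_all be the variance of a patient's mean over all readings, V_post that over post-baseline readings, and c the mean correlation of baseline with post-baseline readings. Power is approximately Φ(d/√(2V/200) - 1.96), where:

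- main effect including baseline: d = 0.25 × 4/5 = 0.20, V = V_all
- post-baseline mean: d = 0.25, V = V_post
- mean change: d = 0.25, V = V_post + 1 - 2c
- baseline-adjusted mean: d = 0.25, V = V_post - c²

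**Worked case, 4 h, ρ = 0.7, s = 0.** V_all = 0.616 and V_post = 0.678; c = (0.7 + 0.49 + 0.343 + 0.240)/4 = 0.443.

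- Main effect: 0.20/√(2 × 0.616/200) = 0.20/0.0785 = 2.55, so power is Φ(0.59) = 72%.
- Baseline-adjusted: V = 0.678 - 0.196 = 0.481 (unrounded inputs); 0.25/0.0694 = 3.60, so power is Φ(1.64) = 95%.

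**Power over 4 h for 0.25 SD** (arm-by-time by simulation with Greenhouse-Geisser correction, the rest by formula):

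| s | ρ | Main effect incl. baseline | Post-baseline mean | Mean change | Arm-by-time, corrected | Baseline-adjusted mean |
|---|---|---|---|---|---|---|
| 0 | 0.5 | 85% | 94% | 69% | 49% | 96% |
| 0 | 0.7 | 72% | 86% | 80% | 60% | 95% |
| 0 | 0.9 | 58% | 76% | 99% | 98% | >99% |
| 0.3 | 0.5 | 73% | 87% | 83% | 65% | 96% |
| 0.3 | 0.7 | 65% | 81% | 92% | 80% | 98% |
| 0.3 | 0.9 | 56% | 74% | >99% | >99% | >99% |

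By simulation the baseline-adjusted mean gives 94-100%, in agreement.

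**Type I error of arm-by-time, identical profiles (simulation).**

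| Window | ρ = 0.5 | ρ = 0.7 | ρ = 0.9 | With Greenhouse-Geisser |
|---|---|---|---|---|
| 0-4 h, uncorrected | 6-7% | 7% | 7-8% | 4-6% |
| 0-48 h, uncorrected | 8-11% | 14-16% | 18-21% | about 5%, within simulation error |

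**Power over 48 h for 0.25 SD.** Corrected arm-by-time: about 7-17%. Main effect: 93-100%. Baseline-adjusted mean: 99-100%. If the baseline reading is left out of the series, a constant shift is invisible to corrected arm-by-time (rejection 4-5% for a 0.3 SD shift).

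**Loss from complete-series analysis.** With a share p of readings missing independently (assumed), the proportion of patients with an incomplete series of k readings is 1 - (1-p)^k.

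| p | k = 5 | k = 48 |
|---|---|---|
| 0.5% | 2.5% | 21% |
| 1% | 1 - 0.99^5 = 4.9% | 1 - 0.99^48 = 38% |
| 2% | 9.6% | 62% |

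Death and ICU discharge would add to this, mostly in the longer window.

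**The case against.** A reader might infer that the planned test rejects a true null two to four times too often and does not test the stated hypothesis at all. The protocol does not support that.

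- It names repeated-measures ANOVA, not the arm-by-time F test, and does not rule out a sphericity correction. The correction restores about 5%, and choosing it is a detail commonly left to the SAP.
- The two- to fourfold inflation needs an uncorrected test over 48 hours. The Aims and the listed haemodynamic outcome use 4 hours, where inflation is modest.
- The arm main effect bears on the hypothesis. Randomisation makes expected baselines equal, so a difference in post-treatment level estimates a difference in rise. It holds its error rate and has good power over 48 hours.
- The same sentence lists the t-test, which could be applied to change values.
- The protocol does not say that incomplete series will be deleted.
- These are secondary outcomes, and the Publication section calls the physiological findings pilot in nature.

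All of this stands, and it limits the point. A sphericity correction answers the error-rate problem but not the low power over 48 hours. Over 4 hours the main effect, the unadjusted post-baseline mean and mean change each lose appreciable power somewhere in the assumed range; the baseline-adjusted mean does not.

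**Conclusion.** The point holds as a poor match of method to hypothesis, not as an invalid test. In the 4-hour window the cost is mainly efficiency: 56-85% power for the main effect including baseline against 94-100% for the baseline-adjusted mean, at 0.25 SD. In the 48-hour window arm-by-time is either inflated (about 8-21%) or weak (about 7-17%), although the main effect still performs well. The tension with intention-to-treat arises only if the classical complete-series form is used; it is small over 4 hours and large over 48.

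All correlations, the effect size and the missing rates are assumptions. Because the method behaves so differently in the two windows, the mismatch between 4 hours and study period matters and should be settled. The primary outcome is not affected. The change is worth making because it is cheap.

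**What to change.** In Data analysis, replace repeated-measures ANOVA for the hourly variables with one between-arm contrast per variable: the mean of post-baseline readings over the first 4 hours after the first study bolus, adjusted for the reading immediately before that bolus and for site. Estimate it in a linear mixed model with serial covariance (AR(1) or spatial power), using all available readings of randomised patients, and report it with a 95% CI. Because the listed outcome is a relative change, the log scale, which the section already allows, would give the contrast as a ratio. Any 48-hour comparison uses the same contrast as a supporting analysis. Arm-by-time becomes descriptive.

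Reconcile the 4-hour window in Aims and Outcome Data with the study-period wording in Hypotheses.

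Cost: a few sentences and a routine model, with no new data. The model assumes a covariance form and data missing at random. An average contrast is less sensitive to a brief transient effect, which the descriptive profile would still show. Any randomised patient who receives no bolus needs a stated time zero.

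### Kaplan-Meier with log-rank is named for in-hospital death and for discharge home, which compete: both curves overstate risk, and the test does not compare hospital mortality

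*Protocol*

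**What the plan says.** The Data analysis section of the protocol names the method outright: "A Kaplan-Meier curve with log-rank test will be performed to further compare in-hospital mortality and rate of discharge home". The word for an additional comparison in that sentence makes the analysis supportive. The same section already provides "Chi-square for categorical data".

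The patient-centred outcomes under Outcome Data list vital status at hospital discharge, discharge destination (home, another hospital or an advanced care institution) and hospital length of stay, for which the date of discharge is recorded. They also list "Mortality status at 90 days". The Kaplan-Meier sentence does not use that 90-day outcome.

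The protocol does not mention competing risks, cumulative incidence, a censoring rule or a time horizon for these curves.

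**The concern.** A patient who goes home can no longer die in hospital, and a patient who dies can no longer go home. Kaplan-Meier for in-hospital death censors patients discharged alive, as though they stayed exposed to the same in-hospital risk as those still on the ward. They left because they were better, so that is untrue. The curve for discharge home likewise treats patients who died, or who went to another institution, as if they could still go home.

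Two things are at stake. First, the plotted curves would be read as the risk of hospital death and the chance of going home, and they estimate neither. Second, the log-rank result would be reported as a comparison of in-hospital mortality, although it also depends on how quickly survivors leave. Discharge timing could differ between arms here: the trial is open label, and the protocol's summary suggests that less fluid may speed recovery.

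**Working it through.** **The plan's own figure.** The protocol gives no event rates and no design figure for these analyses. Its only design figure concerns fluid volume: (1.645 + 1.282)² × (1865² + 1368²) / 485² = 194.8, which matches the stated 195 per group at a one-sided alpha of 0.05. (A two-sided test would need 239; that is a separate matter.) Only the arm size of 200 carries over. Every rate below is an assumption.

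**1. Size of the overstatement.** Take constant hazards, *d* for in-hospital death and *λ* for leaving hospital by any route.

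- Kaplan-Meier risk of death with other exits censored: 1 − exp(−*d t*)
- True cumulative incidence of in-hospital death: (*d*/*λ*) × (1 − exp(−*λ t*))

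*Assumption A:* 20% die in hospital, 60% go home, 20% go elsewhere, median stay 12 days. Then *λ* = ln 2/12 = 0.0578 per day, the death hazard is 0.2*λ* and the home hazard is 0.6*λ*.

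| | Kaplan-Meier | True |
|---|---|---|
| Death, day 28 | 27.6% | 16.0% |
| Death, day 90 | 64.6% | 19.9% |
| Home, day 28 | 62.1% | 48.1% |
| Home, day 90 | 95.6% | 59.7% |

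The two day-90 Kaplan-Meier risks sum to 64.6% + 95.6% = 160%, which is impossible for exclusive events.

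*Assumption B:* death hazard 0.02 and live-discharge hazard 0.08 per day, so *λ* = 0.10. At day 30, 1 − exp(−0.6) = 45% against 0.2 × (1 − exp(−3)) = 19%.

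Over hospital mortality of 10-30% and a median stay of 10-15 days, the day-28 Kaplan-Meier death risk runs from 12% to 44%, against a true 7% to 26%.

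**2. The log-rank test.** Simulation with 200 per arm, day-90 horizon, nominal two-sided 5% level and 20% hospital mortality in the reference arm.

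*Death incidence identical in both arms at every time; only survivors' discharge is faster in one arm.* Two sets of timing assumptions were used: (i) median 8 days to death and 14 days to live discharge; (ii) a mean of 10 days to either exit.

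| Survivors leave | Rejection, censored at discharge | Rejection, kept at risk to day 90 (timing i) |
|---|---|---|
| equally fast | 5% | 5% |
| 1.25 times faster | 9% (i) to 12-13% (ii) | 5% |
| 1.5 times faster | 20% (i) to 31-32% (ii) | 5% |

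Essentially all of the excess rejections show more death in the arm that discharges sooner. The risk set there shrinks faster, so the same deaths are divided by fewer patients. Under timing (i), with discharge 1.5 times faster, the mean day-28 Kaplan-Meier death risk is 27.5% in one arm and 34.7% in the other, against a true 18.2% in both.

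*Death hazard 0.02 per day in both arms; only the discharge hazard rises, from 0.08 to 0.12.* True hospital mortality is 0.02/0.10 = 20% against 0.02/0.14 = 14.3%. The log-rank test rejects in about 5% of trials, so it misses the difference.

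**The case against.** The censoring rule is inferred. The protocol states none, and a statistical analysis plan might keep discharged patients at risk to a fixed day, which would remove the problem. That is fair, but the protocol does name the method and the outcomes. As written, with discharge date the only time variable listed for the hospital outcomes, ordinary Kaplan-Meier is the natural reading.

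The log-rank test is also a valid comparison of cause-specific hazards. That stands. The fault is that the protocol describes it as a comparison of in-hospital mortality, which is a different quantity.

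The analysis is supportive, the primary outcome is fluid volume, and neither the chi-square test on discharge status nor 90-day mortality is affected. That stands too and limits the weight of the point.

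Some stronger readings are tempting but unsupported:

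- *Faster discharge by itself produces a false mortality signal.* It does not if the daily death hazard is unchanged; the test then stays near 5%. Speeding up both exits 1.5-fold gives rejection in about 43% of trials, but the in-hospital death hazard then really differs by a factor of 1.5, so that figure does not measure an artefact of censoring.
- *Mortality is the trial's main safety signal, left unguarded without a monitoring committee.* The protocol lists mortality under patient-centred efficacy, its safety list omits it, and no interim log-rank test is described.
- *Ventilation hours and length of stay share the error.* The Kaplan-Meier sentence does not cover them. How deaths are handled there is unstated, and an analysis plan may settle it.

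**Conclusion.** The method is wrong for its stated purpose, in a supportive analysis. If competing events are censored when they occur, the overstatement of both risks is certain in direction. Its size depends on assumed rates: at about 20% hospital mortality, roughly 28-45% is shown at day 28-30 where 16-19% is true.

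The effect on the test is conditional:

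- With equal discharge timing, it keeps its 5% level.
- With identical death incidence and faster discharge of survivors in one arm, false rejection is roughly 9-13% at 1.25 times and 20-32% at 1.5 times (20% mortality, 200 per arm), against the faster-discharging arm.
- With an unchanged death hazard and a higher discharge hazard, it fails to show a true difference in hospital mortality.

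The documents do not show which of these would apply. The primary result and the proportion-based comparisons are untouched.

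**What to change.** Replace the Kaplan-Meier sentence with three statements:

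1. Kaplan-Meier with log-rank is used for time from randomisation to death from any cause up to day 90. Patients discharged alive stay at risk, and date of death is recorded alongside the 90-day status already collected.
2. In-hospital mortality is compared as a proportion, by the chi-square test already planned.
3. Discharge home is described by cumulative incidence (Aalen-Johansen) and compared by Gray's test, with death and discharge to other destinations as competing events.

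The cost is one extra data field (date of death), a change of wording and slightly more analysis work. No new follow-up is needed.
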